Questionnaire-8, and Athens Insomnia Scale) will be collected at baseline and one-month follow-up.²⁰⁻²⁶

C2 Rationale for the Selection of Outcome Measures

Depression and anxiety can worsen musculoskeletal pain and reduce the effectiveness of traditional orthopedic treatments. Nevertheless, addressing mental health is not currently a part of standard treatment for orthopedic conditions. The purpose of this study is to identify strategies to address mental health in the context of orthopedic care in a manner that is feasible, effective, and acceptable to patients and clinicians.

D Study Design

D1 Overview or Design Summary

This study will utilize qualitative cross-sectional and quantitative longitudinal methods. In semi-structured interviews, orthopedic providers and patients with spine conditions will discuss their overall perspectives, specific needs, and preferred solutions to addressing mental health impairment in the context of orthopedic care and research. In these sessions, patient stakeholders will also user test two specific mental health interventions: a customized version of a commercial digital mental health intervention (Wysa) and a prototype of a print-based mental health resource guide. The patient stakeholders will be provided one month of Wysa access, and they will complete baseline and follow-up measures related to usability, clinical effectiveness, and intermediate behavioral mechanisms through which Wysa is hypothesized to act. Wysa usage data will be obtained from the app company. Delivery of Wysa and the printed resource guide will be iteratively refined based on user feedback.^{13,29,34-42}

D2 Subject Selection and Withdrawal

Inclusion Criteria

- WU Orthopedics patients who are presenting to a spine specialist for neck and/or back pain (spine surgeon, physiatrist, or APP within either of those two divisions) for new or return evaluation
- 18+ years old
- Musculoskeletal pain for 3+ months

Exclusion Criteria

- Routine post-op visit, with no plans for further surgery at this time
- Endorses mental health crisis (active suicidal or homicidal ideation, psychosis)
- Cognitive impairment which would interfere with meaningful engagement with research interview, questionnaires, and/or intervention

2.a Subject Recruitment Plans and Consent Process

Providers:

- Eligible providers are already known, through departmental contacts

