- E-mail will be sent to eligible providers in batches until enough interviews have been scheduled and performed to reach data saturation

- *Verbal consent (waiver of written consent) requested for providers, since they will just be participating in semi-structured interviews.

Patients:

- Prospectively and/or retrospectively review clinic schedules for surgical and non-operative orthopedic spine providers
- To reach purposive sampling goals, some potentially eligible patients may be called prior to appointment date to notify them of the study, assess preliminary interest, and ask to plan staying 60-90 minutes after clinic visit in order to participate in study. Also offer to assist with parking expenses (eg parking validation ticket at CAM).
- Patients will officially be screened at the time of and/or after their orthopedic clinic visit to verify eligibility.
- *Written consent for patients when consent is obtained in clinic. Request the option for verbal consent if the participant is consented over the phone/Zoom.

Contact procedures / permission:

Providers:

- Participants will be e-mailed to be invited to participate.
- They will be asked to complete a brief “demographics” descriptive questionnaire.

Patients:

- Participants will be called or approached in person to be invited to participate.
- During the consent process, they will be asked whether they agree for e-mail and/or text messages to be sent to them. Based on their response, a link to the follow-up REDCap survey will be sent via e-mail and/or text message.

Participants will also be called, e-mailed, and/or text messaged as necessary for reminders to complete the survey.

2.b Randomization Method

No randomization method. No control group.

2.c Risks and Benefits

Risks:

You may experience one or more of the risks indicated below from being in this study. In addition to these, there may be other unknown risks, or risks that we did not anticipate, associated with being in this study.

Although very unlikely, subjects participating in this study may feel inconvenienced from completion of multiple surveys and/or uncomfortable answering some of the survey questions. This risk is minimal because participants will be informed of the estimated time commitment and general content of the survey questions before they consent to participate. The seriousness of this risk is low because participants can withdraw from the study at any time.

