One risk of participating in this study is that confidential information about you may be accidentally disclosed. We will use our best efforts to keep the information about you secure. Please see the section in this consent form titled “How will you keep my information confidential?” for more information.

Benefits:

You will not benefit from being in this study.

However, we hope that, in the future, other people might benefit from this study because information obtained from this study may lead to a better understanding of how to treat patients in an orthopaedic clinic who also experience depression and/or anxiety.

2.d Early Withdrawal of Subjects

If a participant would like to withdraw from this study, they can contact the study coordinator who will document when the patient called to withdraw that their data will not be included in any future data analysis from the time of withdrawal.

2.e Treatment Regimen

After agreeing to participate, patient participants will continue their participation in their orthopedic care plan, as directed by their healthcare provider. We will also assist the participant in downloading the Wysa app to their smartphone or other electronic device, if desired. Through the Wysa app, participants can track and manage their emotions, and they can learn research-based techniques to help them feel better and manage any stress or pain they may be dealing with. Participants will have access to research-based wellness tools such as supportive listening, deep breathing techniques, guided meditation, yoga, and more. Participants can communicate with a virtual artificial intelligence (AI) chatbot, and/or they can message a highly trained and qualified human well-being coach. The intended use of the Wysa app is to encourage mental well-being as an early intervention tool in a self-help context. The Wysa app is considered investigational, which means that it has not been approved by the U.S. Food and Drug Administration.

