- Whenever possible, interviews will occur face-to-face immediately after the participant's orthopedic clinic visit (before the patient has left the clinic)
- If not possible, the participant will be given the option to return to campus for an in-person interview or to complete the study remotely via Zoom. Interviews will be audio and possibly video recorded, using WU-HIPAA Zoom technology, handheld audio recorder(s), and/or other similar device. The recordings will be used to transcribe the interview conversation. After the interview, the recording will then be reviewed by a study team member, and all personal identifiers will be removed prior to being uploaded into Rev.com to be transcribed into text for qualitative analysis.

Contact procedures / permission:

Providers:

- Participants will be e-mailed to be invited to participate.
-

Patients:

- Participants will be called or approached in person to be invited to participate.
- During the consent process, they will be asked whether they agree for e-mail and/or text messages to be sent to them. Based on their response, a link to the follow-up REDCap survey will be sent via e-mail and/or text message. Participants will also be called as necessary for reminders to complete the survey..

Proposed events chart:

Providers:

	Baseline	Follow-up
Intake survey	X	
Interview	X	X (If needed)

Patients:

	Baseline	1 Month
Intake survey	X	
Interview	X	
Usability testing of Wysa and	X	

printed guide		
System Usability Scale (printed guide)	X	
System Usability Scale (Wysa)	X	X
BADS-SF	X	X
CPAQ-8	X	X
Athens Insomnia Scale (AIS)	X	X
PROMIS measures	X (Standard care)	X
Follow-up survey		X

E4 Follow up.

A link to the follow-up REDCap survey will be emailed and/or text messaged to patient participants at one month. These surveys, listed in the chart above, will be the system usability scale (Wysa), BADS-SF, CPAQ-8, Athens Insomnia Scale (AIS), PROMIS measures, and a follow up survey. This will be for the patient participants only, and the only follow up that will occur.

E5 Safety and Adverse Events

5.a Safety and Compliance Monitoring

The research coordinator will document any adverse events reported and review these adverse events with the principal investigator as they arise.

If excessive adverse events are reported, the principal investigator will evaluate whether a participant should be removed from the study to ensure the study participants are not being injured.

5.b Definitions of Adverse Events

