- Suggest that the research places participants or others at a greater risk of harm (including physical, psychological, economic, or social harm) than was previously known or recognized.

5.d Data Collection Procedures for Adverse Events

The research coordinator will document any adverse events reported in a spreadsheet that is password protected and only available to be viewed by the study team.

All adverse events will be reviewed by the principal investigator as they arise.

5.e Reporting Procedures

Events will be reported per the Washington University Institutional Review Board Procedures.

5.f Adverse Event Reporting Period

Events that qualify for immediate reporting described above will be reported within the following timeframe:

- a. 10 working days of the occurrence of the event or notification to the PI or research team of the event.
- b. The death of a research participant should be reported within 1 working day of the occurrence of the event or notification to the PI or research team of the event.

Adverse events/other events that do not require immediate reporting will be provided to the IRB in summary format at the time of continuing review.

F Statistical Plan

F1 Sample Size Determination and Power

No power calculation was performed for this study because the primary aim involves a qualitative analysis. The sample size will be determined by reaching data saturation from the provider and patient stakeholder interviews.

F2 Interim Monitoring and Early Stopping

The Principal Investigator will take responsibility for monitoring patient safety. Patients in the study will be monitored on an as needed basis to assure that they are doing well.

Adverse events will be assessed by [name] to determine if they are serious, unexpected and related to the study procedures.

If a complication should arise, the patient would be previously instructed how to contact the research coordinator.

F3 Statistical Methods

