Interviews will be audio recorded and professionally transcribed. Using inductive and deductive coding approaches based on CFIR and COM-B, a codebook will be developed by one team member, and one or more team members will code all transcripts using NVivo. Group discussion among the research team will be used to resolve coding discrepancies, confirm data saturation has been reached, and organize codes into themes. Scores on the System Usability Scale will be used to iteratively refine both mental health interventions under investigation. Longitudinal PROMIS score changes will be compared between “high” and “low” Wysa users (defined by total Wysa interactions), and associations between changes in behavioral targets (behavioral activation, pain acceptance, sleep quality) and clinical outcomes (depression, anxiety) will be assessed.

G Data Handling and Record Keeping

G1 Confidentiality and Security

Plans to protect the privacy interests of the participants during the conduct of the study:

- 1) Only the minimum necessary private information is collected for the purposes of the study
- 2) Any procedures or interventions conducted as part of the study will be conducted in private setting to the extent possible
- 3) Recruitment/consent will occur in a private setting
- 4) Participants will be able to ask questions in a private setting

Project uses paper and hard copy consents, surveys, data collection forms, research subject binders, or other hard copy materials:

- 1) All materials are stored in secured environment
- 2) Access is limited to research team members only
- 3) Transported securely/shipped with tracking mechanism

Project collects, stores and/or transmits electronic data on mobile devices, desktop computers, servers including cloud servers, email, or any other information in electronic form:

- 1) Password protected
- 2) Access is limited to research team only
- 3) Data in Redcap
- 4) Data in Box
- 5) eCRF system
- 6) Transmitted using recognized security for electronic submission
- 7) Recordings taken during interviews with providers and patients will be reviewed by a study team member, and all personal identifiers will be removed prior to being uploaded into Rev.com to be transcribed into text for qualitative analysis.
- Other

G2 Training

Study coordinator was trained in the Wysa software, and is able to explore the app with the participants in the patient population for use on their own. No formal training is necessary for this study.

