G3 Records Retention

All research data will be retained in a locked office in a locked cabinet for 10 years after the closure of the study.

H Study Administration

H1 Funding Source and Conflicts of Interest

This study is funded by a WU Center for Perioperative Mental Health R03 Pilot and Feasibility Award. The study start date was 12/1/2021.

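### Does the withdrawal rule in section 2.d put the analysis at risk by leaving unclear whether data already collected are kept?

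*Combined protocol and SAP*

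**What the plan says.** Section 2.d (Early Withdrawal of Subjects) is the only rule in the supplied text on the data of people who withdraw. A person who wants to leave is told that "they can contact the study coordinator who will document when the patient called to withdraw", and the sentence ends by stating that "their data will not be included in any future data analysis from the time of withdrawal". It does not separate data gathered before withdrawal from data gathered after.

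Four other places bear on it:

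- **2.c (Risks and Benefits), repeated under 5.c:** "participants can withdraw from the study at any time". There is no cut-off after which an interview is safe from withdrawal.
- **F1 and F3:** "The sample size will be determined by reaching data saturation from the provider and patient stakeholder interviews", and the team meets to "confirm data saturation has been reached". F3 defines no analysis set and gives no rule for withdrawals or missing one-month data.
- **G3, on how long records are kept:** "All research data will be retained in a locked office in a locked cabinet for 10 years after the closure of the study". No exception is made for withdrawers, so 2.d appears to govern use in analysis, not deletion.
- **D1:** "Wysa usage data will be obtained from the app company". These logs are not in the events chart, and 2.d does not mention them.

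**The concern.** Two analysts following 2.d could build different datasets. If the closing phrase modifies the analysis, any analysis run after the withdrawal date omits everything the person gave. If it modifies the data, only later material is unused. The first is the more natural reading, because the data are unqualified and the time phrase directly follows the mention of future analysis.

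The first reading would fall mainly on Aims 1 and 2. Patient interviews and usability testing take place only at baseline, and Aim 1 sets the sample size through saturation. An interview already counted toward saturation could leave the analyzed set after recruitment has closed. Usability feedback could shape the iterative refinement and then be missing from the final summary. Results could depend on whether an analysis was run before or after someone withdrew.

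**Working it through.** The plan gives no sample size, withdrawal rate or power figure, so there is no stated result to reproduce. What can be checked is how much each reading removes per person, and which aim that touches.

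**Inputs: the patient events chart in E3**

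- Baseline marks: intake survey, interview, usability testing, System Usability Scale (SUS) for the printed guide, SUS for Wysa, BADS-SF, CPAQ-8, Athens Insomnia Scale, PROMIS = 9. The PROMIS entry is marked as standard care.
- One-month marks: SUS for Wysa, BADS-SF, CPAQ-8, Athens Insomnia Scale, PROMIS, follow-up survey = 6.
- Total: 9 + 6 = 15.

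**Loss per patient, by timing**

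| Situation | Collected | Dropped if all data are removed | Dropped if only later data are removed | Change score available? |
|---|---|---|---|---|
| Active withdrawal after Visit 1, before the one-month survey | 9 | 9 of 9 | 0 of 9 | No, on either reading |
| Active withdrawal after the one-month survey | 15 | 15 of 15 | 0 of 15 | Only on the second reading |
| No response at one month, no contact with the coordinator | 9 | 0 (2.d not triggered) | 0 (2.d not triggered) | No |

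The denominator in the first row has to be 9. Dividing by all 15 scheduled items would give 9/15 = 60%, but the 6 one-month items never exist for that patient on either reading. These are counts of chart entries and do not measure information; one PROMIS entry, for example, covers several scales.

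**What this means for each aim**

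1. *Aim 3.* F3 compares PROMIS changes between high and low Wysa users and relates changes in behavioral targets to changes in depression and anxiety. Both need two time points. A patient who leaves before the one-month survey contributes to neither, whichever reading applies. The readings differ only for someone who withdraws after that survey. By then the month of app access and the only patient follow-up (E4) are over, so there is little left to withdraw from except use of the data.
2. *Wysa logs.* Use logged before an early withdrawal has no PROMIS change to pair with. It could matter for describing engagement, or if the high/low cut were set on everyone with logs; F3 does not say how the cut is set.
3. *Aim 1.* Saturation is a judgment the team makes during coding. Provider invitations go out in batches until it is reached (2.a), and the patient sample is also set by saturation (F1). While recruitment is open, a lost interview can be replaced. The exposed case is a withdrawal after recruitment closes, and nothing in the documents shows that this happens.
4. *Aim 2.* Refinements already made from a participant's feedback are not undone. Only the later summary of usability scores would lack that person.

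Total loss is the number of active withdrawals times 9 or 15. That number is not given and may be zero.

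**The case for a change.** The strongest case for a change is that the primary aim rests on the interviews, the sentence is ambiguous, and one sentence would settle it: keep data collected before withdrawal, including app logs, unless the participant asks for removal. That needs no new data collection, and a reader could then tell which dataset was analyzed.

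The ambiguity stands. So does the point that a report should state how many people withdrew and when, which is possible because the coordinator records each withdrawal.

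The proposed default is less secure. On its more natural reading 2.d already answers the question, by excluding the person from later analyses. For recorded interviews about mental health this is a reasonable protection, and replacing it with retention unless removal is requested is a choice of policy, not the correction of an error. H1 gives a start date of 12/1/2021, so anyone already enrolled joined under the present rule, and a new default could apply to them only as far as their consent allows. Consent pages were not available here, and 2.c and 5.c contain text carried over from a consent form, so terms on data use may exist there. The gain is also small where it is said to matter most: a patient who withdraws after the one-month survey could still have the data removed on request under the alternative wording.

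**Conclusion.** No change to the plan is called for. The sentence in 2.d is clumsy and does allow two readings, but the study's conclusions stay sound on either. Per active withdrawer the difference is 9 of 9 collected items before the one-month survey and 15 of 15 after it, against none on the second reading. It falls mainly on the baseline interview and usability data, and reaches Aim 3 change scores only through withdrawal after follow-up. No bias or direction of bias is shown. This is a single-cohort pilot with a qualitative primary aim and no power calculation, so no stated error rate or precision is affected.

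This rests on four assumptions: active withdrawals are few; the team applies one reading throughout, in line with the consent terms; withdrawals are counted in the report; and saturation is looked at again if an interview is lost. A competent team would do the last three without further instruction. If several interviewed patients withdrew after recruitment closed, the saturation claim would need a second look, but the documents give no sign of this.

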Depression and anxiety worsen musculoskeletal pain and reduce the effectiveness of traditional orthopedic treatments. Nevertheless, addressing mental health is not currently a part of standard treatment for orthopedic conditions. The purpose of this study is to identify strategies to address mental health in the context of orthopedic care in a manner that is feasible, effective, and acceptable to patients and clinicians.

C Study Objectives

C1 Primary Aim

Aim 1: Identify the contextual determinants of implementation success for addressing patients' mental health in the context of orthopedic care.

Using standard qualitative methods, two stakeholder groups will be interviewed: WU orthopedic providers and orthopedic spine patients ≥ 18 years old, with a focus on patients 65 years and older. Using purposive sampling, a goal of at least half of patient stakeholders will be women, and one quarter will identify as an under-represented minority. In semi-structured interviews guided by the Consolidated Framework for Implementation Research (CFIR) and the COM-B model of behavior change, providers and patients will describe needs and preferences related to addressing mental health in a clinical and research context (e.g., recruiting and retaining orthopedic patients in a mental health related randomized controlled trial).

Aim 2: Conduct usability testing for two mental health interventions which can feasibly be implemented in a real-world orthopedic setting: a digital mental health intervention (Wysa) and a novel printed resource guide.

Using semi-structured interviews and the System Usability Scale (SUS), orthopedic patients will participate in an iterative user design process to refine the delivery of Wysa and a printed guide of local and online mental health resources. The printed guide is being prepared as an “enhanced usual care” control intervention for a subsequent R01 randomized controlled trial proposal.^{17,18}

Aim 3: Identify the intermediate mechanisms through which a digital mental health intervention (Wysa) improves mental health symptoms in orthopedic patients.

In a pilot prospective cohort study, patients will receive one month of access to Wysa. Measures of clinical effectiveness (self-reported PROMIS Depression, Anxiety, Pain Interference, and Physical Function¹⁹) and hypothesized behavioral targets (Behavioral Activation for Depression Scale-SF, Chronic Pain Acceptance

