The study PI ([name]) is one of over 15 spine care subspecialists within the WU Department of Orthopaedic Surgery. She and her colleagues manage patients with a range of sociodemographic backgrounds at multiple clinic sites across the St. Louis metro region including the Barnes-Jewish Center for Advanced Medicine, Barnes-Jewish Hospital Center for Outpatient Health, Barnes-Jewish West County Hospital, and the Barnes-Jewish Center for Advanced Medicine – South County. Furthermore, all of the WU Orthopedics spine patients complete depression and anxiety measures as standard care during each clinical encounter (PROMIS CAT Depression and Anxiety), and [name] research coordinator has specifically enrolled older adult orthopedic patients with spine conditions into mental health related research studies by using these measures as screening items. This patient base and the mental health screening measures will facilitate seamless recruitment of patient stakeholders with a range of self-reported depression and anxiety symptom severity. Additionally, [name] and several other spine providers have adequate clinical space to allow patient rooms to be used for research during clinic hours, and her team has experience recruiting, consenting, and enrolling patients into research studies in person and virtually (via phone or Zoom-HIPAA), from her own clinics and from those of her clinical colleagues. The in-person and virtual participation options will allow patients to participate in the semi-structured interview and usability testing in whichever format is preferred. When convenient for the participant, study recruitment, consent, and the interview can be completed within approximately one hour of the patient's clinical encounter.

E2 Schedule of Measurements

E3 Visit 1

Providers:

- Interviews will occur face-to-face (in a private room) or via Zoom, whichever the participant prefers. Interviews will be audio and possibly video recorded, using WU-HIPAA Zoom technology, handheld audio recorder(s), and/or other similar device. The recordings will be used to transcribe the interview conversation. After the interview, the recording will then be reviewed by a study team member, and all personal identifiers will be removed prior to being uploaded into Rev.com to be transcribed into text for qualitative analysis.

Patients:

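### The clinic PROMIS score may both guide whom to approach and serve as the baseline, so regression to the mean can enter the F3 change scores with nothing planned to reveal it

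*Combined protocol and SAP*

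**What the plan says.** - **Recruitment.** E1 (Screening for Eligibility, patient stakeholders) says that all spine patients "complete depression and anxiety measures as standard care during each clinical encounter (PROMIS CAT Depression and Anxiety"). It then says that the patient base and the "mental health screening measures will facilitate seamless recruitment of patient stakeholders with a range of self-reported depression and anxiety symptom severity". It gives no cut-off, quota or direction.
- **Routes.** Section 2.a lists, for patients: "Prospectively and/or retrospectively review clinic schedules for surgical and non-operative orthopedic spine providers". It also allows some patients to be phoned before their appointment, and places formal screening at or after the visit.
- **Baseline.** The patient events chart under E3 has the row "PROMIS measures X (Standard care) X". PROMIS is the only measure in that chart whose baseline comes from standard care. BADS-SF, CPAQ-8 and the Athens Insomnia Scale are plain study entries at both times.
- **Comparator.** Sections 2.b and 2.f state that there is no control group.
- **Analysis.** F3 compares PROMIS change between high and low Wysa users, and relates changes in the behavioral targets to depression and anxiety. It mentions no adjustment for baseline PROMIS.

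**The concern.** A score observed on one day is the patient's usual level plus transient fluctuation and measurement error. If a patient is approached because that score is high, the error is on average positive. If the same score is then the baseline, the one-month score is expected to be lower even if Wysa does nothing. The reverse holds for patients approached because of a low score.

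This is most plausible for patients screened at the visit or found by looking back through clinic schedules. On those routes the score a recruiter can see is naturally the visit score that becomes the baseline. Same-day participation does not remove the problem, because the error is already in the reading.

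Aim 3 is meant to supply planning data for a later trial. Apparent improvement that comes partly from selection, or a user-group difference that comes partly from different baselines, could mislead that planning.

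**Working it through.** The documents give no sample size, SD, retest correlation or expected change, so there is no plan figure to reproduce. The check asks how large the artefact could be.

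**Assumed inputs (not in the documents):** clinic mean T-score 50, SD 10, bivariate normal scores, and correlation r between baseline and one month of 0.6 to 0.9.

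**Formula.** Expected mean change from regression alone = −(1 − r) × (mean baseline of those recruited − clinic mean).

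**1. Score not used to choose patients.** The recruited mean equals the clinic mean, so the change is −(1 − r) × 0 = 0 at every r.

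**2. Symmetric range: equal numbers below 45, 45 to 55, and above 55.**
- The outer bands have means 10 × 0.3521/0.3085 = 11.4 points below and above 50; the middle band is at 50.
- The outer bands move by 0.4 × 11.4 = 4.6 points (r = 0.6) or 0.1 × 11.4 = 1.1 points (r = 0.9), upward in the low band and downward in the high band.
- The average is 0.

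**3. Range tilted to high scores: equal numbers below 55, 55 to 60, and 60 or more.**
- Below 55: −10 × 0.3521/0.6915 = −5.1 from the clinic mean.
- 55 to 60: 10 × (0.3521 − 0.2420)/(0.8413 − 0.6915) = +7.3.
- 60 or more: 10 × 0.2420/0.1587 = +15.2.
- Mean displacement: (−5.1 + 7.3 + 15.2)/3 = 5.8.
- Artefact: −0.4 × 5.8 = −2.3 points (r = 0.6) to −0.1 × 5.8 = −0.6 points (r = 0.9). Simulation of 2,000,000 patients at each r gave −2.32 and −0.59.

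**4. High versus low user contrast.** Spurious difference in change = (1 − r) × (baseline gap between the groups).

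| Baseline gap (assumed) | r = 0.6 | r = 0.9 |
|---|---|---|
| 0 | 0 | 0 |
| 2 points | 0.8 | 0.2 |
| 5 points | 2.0 | 0.5 |

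**5. Association of target change with depression and anxiety.** The same artefact enters if baseline PROMIS is related to change in the targets. The documents give nothing from which to size this.

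**The case against.** The strongest objection is that the protocol contains no selection rule on PROMIS.
- The D2 inclusion criteria are a spine clinic visit, age 18 or over, and "Musculoskeletal pain for 3+ months".
- The purposive targets in C1 are "a goal of at least half of patient stakeholders will be women, and one quarter will identify as an under-represented minority", with a focus on age 65 and over.
- The E1 remark that the coordinator has enrolled patients "into mental health related research studies by using these measures as screening items" describes past studies.
- The 2.a line on reviewing schedules concerns schedules, not scores.

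All of this stands. A reader might infer that regression to the mean is built into the change scores, or that recruited patients will appear to improve by 4.0 to 1.0 points, which is (1 − r) × 10 for a group averaging 10 points above the clinic mean. The documents do not support that. They aim for a range, state no direction, and F3 lists no test of cohort mean change.

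Three further points also stand.
- Patients phoned before the visit may have been picked on an earlier encounter's score. Part of the regression would then occur before the baseline is taken.
- In any pre-post study with r below 1, change correlates negatively with baseline. Reuse of the recruitment score is therefore not what makes the user contrast vulnerable; a baseline gap between user groups is.
- Interviews take place straight after the clinic visit where possible, so a repeat PROMIS shares that day's state and removes only part of the error.

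The objection does not dispose of the point. The E1 sentence on a range of severity is about this study, and the scores can help obtain that range only if someone looks at them. Participants use Wysa as much or as little as they like (2.e), so usage may follow severity. Nothing in F3 would show or remove the result.

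**Conclusion.** The concern holds as a conditional risk. A clinic PROMIS score may guide approach and also supplies the baseline, with no separate study baseline, no control group and no stated baseline adjustment. Regression to the mean can therefore enter the F3 change scores; the documents do not establish that it must, or in which direction.

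- **Mean change:** zero without score-guided approach or with a symmetric range (although the outer bands still move in opposite directions); about 0.6 to 2.3 points of false improvement with the illustrative tilted range.
- **High versus low users:** zero without a baseline gap; about 0.5 to 2.0 points for a 5-point gap.

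These figures rest on the assumed clinic mean, SD, correlation, bands and gaps. Severity is low to moderate: the primary aim is qualitative, no power calculation was made, and Aim 3 is a pilot cohort. The change is still worth making because it is cheap and the results feed a later trial.

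**What to change.** 1. In the patient events chart, change the baseline PROMIS entry from standard care to study-collected. Have every patient complete PROMIS Depression and Anxiety with the intake survey, before Wysa access.
2. In F3, name that score as the baseline for PROMIS change, and adjust both the user comparison and the target-outcome associations for baseline PROMIS.
3. In E1, state whether and how clinic PROMIS scores guide whom to approach.
4. State in F3 that uncontrolled mean change will not be read as a Wysa effect.

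The cost is a few minutes of patient time plus chart, E1 and F3 wording; the intake survey already exists and PROMIS is already in the one-month survey. The repeat score helps most when the interview is later than the clinic visit. For same-day interviews it removes only part of the artefact, which is why the adjustment is needed as well. Adjustment deals with the baseline gap if both user groups regress toward a common mean. It does not make a comparison by self-chosen usage a causal one.
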